1.0 Introduction and Background

Cancer poses challenges to physical, emotional, and social well-being. Concerns such as health anxiety, depression, reduced social connectivity, and acute stress, often in the form of trauma, thread across all diagnostic groups and can become threats to vitality. Researchers found that 25% of American cancer survivors reported poor physical health-related quality of life (HRQOL) and 10% of cancer survivors reported poor mental HRQOL; in comparison, the non-cancer adult population was 10% and 6%, respectively (Weaver et al., 2012). Impacts can be long lasting. Colorectal cancer survivors, for example, are at an increased risk for adjustment, anxiety, and substance-related disorders, delirium, dementia, body image concerns, and sexual dysfunction five years post-diagnosis (Lloyd et al., 2019). Cancer-related financial toxicity has been associated with higher levels of depressed mood, increased concerns about cancer recurrence, and an overall reduction in HRQOL (Kale & Carroll, 2016).

The SARS II COVID-19 pandemic has infected millions of individuals and killed hundreds of thousands. Navigating cancer survivorship in the midst of a pandemic further complicates coping processes and normal avenues of support. Cancer survivors commonly contend with reduced immune functioning, placing many at higher risk for viral contagion and/or comorbidities. Many are advised to seek an even greater degree of social isolation. Researchers have analyzed data from the outbreak in China and found that cancer survivors presenting with COVID-19 face a higher risk of being admitted to an intensive care unit, being placed on a ventilator, or death than non-cancer patients presenting with COVID-19 (Liang et al., 2020). The presence of routine medical appointments and existing financial distress may position them to make complex decisions regarding their safety and behaviors during such a stressful time.

While most global citizens have not endured a pandemic, data from recent epidemics can be informative as to psychological impacts. Researchers studying post-epidemic conditions have described the former SARS outbreak as a “mental health catastrophe,” with post-traumatic stress disorder (PTSD) as the most commonly noted psychiatric condition, followed by depressive disorders (Liang et al., 2020). Wu et al. (2005) found that people who perceived life threat during the SARS epidemic experienced anxiety, whereas depression was significantly associated with knowing someone who tested positive for SARS; the researchers also identified gender and education levels to be associated with avoidance symptoms. In 2009, researchers exploring long-term psychiatric comorbidities among SARS survivors urged preparedness among health care professionals to detect and respond to the psychological sequelae that co-exist with infectious disease outbreaks (Mak et al., 2008). Cancer survivors working to navigate disease survivorship and dynamic pandemic conditions then may be at even higher risk for emotional distress and trauma.

In our current world, internet usage has become ubiquitous. In 2019, virtually all young adults (YAs) used the internet (100% of 18-29 year olds and 97% of 30-49 year olds) and the majority of middle aged (88% of 50-64 year olds) and older adults (73% of those 65+) adopted this technology as well (Pew, 2019). Many people already use the internet as their primary source of health information, although only around 33% of adults have engaged in internet-based doctor-patient communication (Haluza et al., 2017). During the COVID-19 pandemic, more than half of U.S. adults (53%) have reported that the internet has been essential (Vogels et al., 2020). Furthermore, 64% of U.S. adults endorsed that the internet/phones will be useful but not a replacement for in-person contact, while 27% rated that it will be just as good as in-person contact (Anderson & Vogels, 2020).

Cancer within a Pandemic: A Telemental Health Intervention Designed to Augment Psychological Resilience amidst Dual Health Threats

Wake Forest Baptist Comprehensive Cancer Center
WFBCCC #01520

This indicates that many Americans are open to utilizing virtual methods in lieu of in person contact at this time. Therefore, utilizing effective online methods for mental health treatment behoves researchers and clinicians alike, now more than ever. Online group counseling is considered to be accessible and cost-effective, and it also eliminates the risk of in-person contact between providers and other patients.

During the COVID-19 pandemic, it is reasonable to think that patients who have little to no experience with internet-based doctor-patient communication are rapidly being forced to adapt to these technologies. Cancer survivors in particular may find virtual telehealth interventions especially attractive due to the increased likelihood of exhibiting an immune-compromised status as well as the need to contend with frequent medical appointments that take them away from other responsibilities routinely. Particular sub-groups, including adolescent and young adults, rural or geographically distant, and economically distressed survivors, may find this modality especially inviting due to familiarity or enhanced access to care. YAs are considered to be digital natives because they have grown up in the digital age using the internet and computers, while digital immigrants are those who were not born into the digital world but rather adopted it at some point during their lifespan (Prensky, 2001). This distinction may be important in how users interact with, utilize, and adapt to technology use and online services. Recent research supports that digital immigrants (i.e., middle and older age adults) need additional coaching of how to use a technology than digital natives (Kasharwani, 2020). Additionally, digital natives were found to be more skeptical of the reliability of online health information and the reasonability of health information exchanged between providers and patients (Haluza et al., 2017). Thus, digital natives are a group that are able to adapt readily to the use of new technologies in novel contexts and they may better understand potential risks of utilizing an online platform.

This supports that focusing on a YA group for an initial study of the feasibility of an online group therapy for cancer patients is reasonable. Additionally, having a group with a higher baseline knowledge of technology as well as higher rates of skepticism of online platforms may lead to helpful feedback for future iterations of the group that will target additional patient populations. The SARS-II COVID-19 pandemic has served as a catalyst for requisite social distancing as well as increased familiarity with virtual meetings for those with the technological capacity.

Such a shared technological shift might make this type of group offering more feasible and attractive to prospective participants within the present circumstances. In response to the psychological vexations posed by simultaneous cancer and pandemic survivorship, we propose to create a virtual pandemic support group for cancer survivors that targets the constructs of health anxiety, depression, trauma, and social connectivity. The use of Acceptance and Commitment Therapy (ACT) (Arch & Mitchell, 2016) and Logotherapy (Mohabbat-Bahar et al., 2014) with cancer survivorship groups has demonstrated promising results, including the reduction of anxiety, depression, fatigue, fear of cancer recurrence, physical pain, and trauma-related symptoms, while also increasing meaning and purpose in life and a feeling of regaining some control over one's life. In line with the guiding principles of ACT and Logotherapy, this group will focus on coping strategies that enable positive psychosocial outcomes: Acceptance of cancer-related distress, reduction of cancer-related avoidance, identification of personal values, a commitment to making meaningful changes in one's behavior, and identifying meaning and purpose in life (Arch & Mitchell, 2016; Mohabbat-Bahar et al., 2014).

This will be a closed Young Adult (YA) group for the purposes of strategically covering essential skills needed for psychological flexibility, resilience, and meaning-making within these concurrent challenges to health. Pre-

Cancer within a Pandemic: A Telemental Health Intervention Designed to Augment Psychological Resilience amidst Dual Health Threats

Wake Forest Baptist Comprehensive Cancer Center
WFBCCC #01520

and post-intervention assessments will assess change over time across a variety of variables, and researchers will analyze trends in self-selection and attrition to inform future interventions.

Psychosocial oncology providers within a comprehensive cancer center have the responsibility to assess and respond to the dynamic mental health needs of those navigating cancer care within their communities. A pandemic both augments the need for and complicates the provision of mental health care. Demand and need for psychological care intensifies while factors impeding in-person provision of care also multiply. To cater to the mental health needs of cancer survivors within evolving pandemic conditions, we plan to open groups that allow access to survivors coping with similar challenges. By offering carefully constructed virtual groups that target psychological symptoms and coping skills applicable to these dual health threats, we aim to empower and support the development of transferable coping skills within YA cancer survivors within our community. It is our hope that improved psychological flexibility will result in improved coping within their cancer care and pandemic responses.

2.0 Hypotheses:

Participants will demonstrate improvements in:

self-efficacy, psychological flexibility, resilience, social connectivity, sense of purpose and meaning

Participants will demonstrate reductions in:

loneliness, anxiety, depression, helpless/hopeless feelings

2.1 Primary Objective(s)

2.1.1 To improve self-efficacy for young adult cancer survivors navigating pandemic conditions

2.2 Secondary Objective(s)

2.2.1 To reduce depression and anxiety levels through meaning-making.

2.3 Exploratory Analyses:

2.3.1 To assess the feasibility of conducting a telehealth support group for cancer survivors within a pandemic.
2.3.2 To assess YA cancer survivors' interest in participation in a telehealth support group within a pandemic.
2.3.3 To enhance participants' strategies for engaging social connectivity and reduce feelings of loneliness amidst simultaneous forces promoting self-isolation (i.e., cancer diagnosis and pandemic).

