6.0 Intervention Plan

The study aims to initially recruit a single cohort of 15 patients. This is a virtual group interventional design in which investigators distribute the electronic assessment battery, perform the intervention, assess mid-way through, and reassess post-intervention. The virtual group will be conducted within a secure platform such as Microsoft WebEx. Assessments (pre-, post-, mid-way) will be distributed through REDCap, a secure virtual platform, as will session handouts and forms. If participants do not have headphones, these will be provided by the study team. The biostatistician will assist with the assessment of change over time within the instrumentation. The session content for this group is built on clinical experience and empirically informed practices, drawing upon elements of Acceptance and Commitment Therapy and Meaning Making approaches. Investigators/facilitators believe that in these unique times, it is optimal to pull elements from various (manualized) approaches that contribute important elements to the group experience. In short, we are making intentional decisions within session design in which we draw heavily from empirically supported practices yet combine them in a manner that seems appropriate for the circumstances based on clinical judgment.

The intervention will be conducted by graduate-prepared mental health providers who are licensed or working under the supervision of a licensed provider. Providers will co-facilitate at all times, with two providers available to respond to group dynamics and follow up with individual members as needed.

The clinicians leading the group will adhere to professional, legal, and ethical guidelines of confidentiality established by professional organizations and state law. Legal and ethical exceptions to confidentiality include: A clear or present danger that the patient intends to harm her/himself or another, knowledge of the abuse or neglect of a minor child or incapacitated adult, or responses to a court subpoena or as otherwise required by law. All members of the group will be required to sign confidentiality forms, in which they agree not to disclose

Cancer within a Pandemic: A Telemental Health Intervention Designed to Augment Psychological Resilience amidst Dual Health Threats

Wake Forest Baptist Comprehensive Cancer Center
WFBCCC #01520

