6.1 Methods

Steps: (Conducted by the Psychosocial Oncology group)

1. Advertise and Identify Prospective Candidates
2. Screen all referred candidates on rolling basis
3. Send out pre-group assessments electronically for completion
4. Begin eight weeks of group work
5. Send out post-group assessments electronically for completion

Session Content

Adapted from Eilenberg, Frostholm, & Kronstrand 2014 with elements on meaning making from Breitbart & Poppito, 2005, rev. 2011:

Session 1: Introduction to ACT and Meaning Making

Summary: The purpose of the 1st session is to introduce the framework and form of the group, as well as expectations for the 8 sessions. Our main focus is on willingness to engage in treatment, a basic understanding of ACT, mindfulness, and the importance and sources of meaning making—creative, experiential, historical, and attitudinal. We will start to practice experiencing each from this first session. The purpose is to introduce the framework of the group, logistics, and to create a safe and accepting atmosphere. Furthermore, we will briefly introduce participants to an understanding of what health anxiety in the context of cancer is.

Session 2: Previous strategies for Anxiety Control

Summary: The purpose of this session is to examine the individual's control strategies and experiences in coping with health anxiety. We will introduce the concept of pain vs. suffering and how cancer can enhance life meaning, maintain life meaning, or create loss of meaning. The purpose is to help the individual to examine whether the previously used strategies have been effective in the short- and long-term in relation to living a values-based, meaningful life.

Session 3:Introduction to Values Based Living

Summary: The purpose of session 3 is to extend the insights and experiences from the last session in relation to the control agenda's limited effect on anxiety. Through experiential exercises, the effect of the control agenda is further tested and examined. Further, values-based living is introduced as an alternative to an avoidance and control-driven life. Values are introduced in the context of willingness and a discussion will introduce "Life as Legacy" both in the past, the here-and-now, and the future.

Session 4: Acceptance as an Alternative to Control

Cancer within a Pandemic: A Telemental Health Intervention Designed to Augment Psychological Resilience amidst Dual Health Threats

Wake Forest Baptist Comprehensive Cancer Center

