This self-report questionnaire has 20 items that measure a person's sense of purpose and meaning in life and is based on Viktor Frankl's Logotherapy (Davies et al., 2014). Good reliability has been found, with split-half reliability coefficients of .90.

Pre-screening questionnaire

This investigator-created instrument is designed to assess group suitability, with attention to inclusion and exclusion criteria. It also will include technology training for group technology requirements.

Group Evaluation Questionnaire

This investigator-created instrument is designed to assess satisfaction and solicit feedback. It also will have questions pertaining to engagement with other group members exterior to group meetings.

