9.2 Analysis of Secondary Objectives

To reduce depression and anxiety levels through meaning-making, three instruments will provide information on baseline, Visit 8, and change over time. The CAS, MINI MAC, and Purpose in Life Test will all be utilized to estimate depression and anxiety levels. With an n of 15, the width of the confidence interval around the baseline, Visit 4, Visit 8, and change between baseline and Visit 4 as well as Visit 8 scores would be approximately 1.02 standard deviations; a paired t-test will be used to assess the change in the scores. As this is a pilot study, no adjustment in the p-value will be done for multiple comparisons.

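### Objective 2.2.1 credits any fall in depression and anxiety to meaning-making, although meaning-making is delivered only in a package with ACT and section 9.2 counts the Purpose in Life Test as a symptom measure

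*Combined protocol and SAP*

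**What the plan says.** Section 2.2.1 of the combined protocol and SAP gives the secondary objective as "To reduce depression and anxiety levels through meaning-making". The same wording returns as the secondary outcome (item 5.1.2, under 5.2) and opens section 9.2.

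The design is one group without a comparator: "The study aims to initially recruit a single cohort of 15 patients" (6.0). The content is described as "drawing upon elements of Acceptance and Commitment Therapy and Meaning Making approaches" (6.0), and the two are combined from the start: "Session 1: Introduction to ACT and Meaning Making" (6.1 Methods).

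Section 6.2 describes the Purpose in Life Test as measuring a person's "sense of purpose and meaning in life". Section 2.0 puts meaning among the things expected to rise ("self-efficacy, psychological flexibility, resilience, social connectivity, sense of purpose and meaning"), and lists anxiety and depression separately among the things expected to fall. Table 1 and section 9.2, however, place the Purpose in Life Test beside the Coronavirus Anxiety Scale (CAS) and the Mini-MAC as one of three instruments for the level of depression and anxiety. The planned test is that "a paired t-test will be used to assess the change in the scores" (9.2). No section relates change in one of these scores to change in another.

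**The concern.** Two things in the plan do not fit together.

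First, the objective credits one component, but every participant gets both. Acceptance, defusion and the observing self are taught alongside the legacy and meaning work. Section 1.0 also names another possible route, the hope that greater psychological flexibility will lead to better coping. Flexibility has its own scale, the AAQ, analysed in 9.3.4.

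Second, the only scale for meaning is counted as a symptom scale. Purpose in Life could rise while the CAS and Mini-MAC stay flat, and 9.2 would allow that rise to be reported as progress on depression and anxiety. Conversely, symptoms could fall mainly in people whose sense of meaning did not change, and the result would still sit under an objective that credits meaning-making.

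What is at stake is the wording of the secondary conclusion. The symptom estimates themselves are not affected.

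**Working it through.** **1. What the plan's own figure covers.** Sections 9.1 to 9.4 give a confidence interval width of about 1.02 SD for n = 15. With the normal quantile, the full width is 2 × 1.96/√15 = 1.012 SD. The half-width is 0.506, which rounds to 0.51 and doubles to 1.02, so the figure reproduces. With the t quantile (14 df) the width is 1.108 SD. The paired t-test at n = 15 has 80% power, two-sided 0.05, for a mean change of about 0.78 SD of the change scores. These figures all describe one score at a time. None concerns a link between meaning and symptoms.

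**2. What separate paired t-tests can show.** For each scale, t = mean change/(SD of change/√n). The Purpose in Life statistic uses only Purpose in Life changes, and the CAS statistic only CAS changes. If the 15 Purpose in Life changes were reassigned among the participants, both t statistics would be identical, while the correlation between the two sets of changes could move from strongly negative to strongly positive. The t-tests therefore show whether mean meaning rose and whether mean symptoms fell. They do not show whether this happened in the same people.

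**3. What an added correlation of changes could show.** Inputs: n = 15 (6.0, 9.4); the values of r are assumptions, because the documents give none. The interval is tanh(atanh(r) ± 1.96/√(n - 3)).

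- r = 0.50, n = 15: 0.549 ± 1.96/√12 = 0.549 ± 0.566, that is -0.017 to 1.115, which back-transforms to -0.02 to 0.81.
- r = 0.30, n = 15: -0.25 to 0.70. r = 0.70, n = 15: 0.29 to 0.89.
- r = 0.50 with 12 completers (assumed): -0.10 to 0.83. With 10 (assumed): -0.19 to 0.86.
- True r needed for 80% power, two-sided 0.05: tanh(2.80/√12) = 0.67 at n = 15, 0.73 at n = 12 and 0.79 at n = 10.

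The sizes are given as positive. If meaning rises as symptoms fall, the sign is negative and each interval is mirrored.

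**4. What such a correlation could not show.** Assume no pathway and no treatment effect, only mood on the day, independent between occasions, that makes Purpose in Life (P) and anxiety (A) correlate -0.5 at each assessment, with unit variances.

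- Baseline-to-post changes: covariance = 2 × (-0.5) = -1, each variance = 2, so r = -0.50 with no pathway at all.
- P change from baseline to mid-point against A change from mid-point to post: only the mid-point is shared, so covariance = -(-0.5) = +0.5, each variance = 2, and r = +0.25. Same-occasion correlations of -0.3 to -0.7 give +0.15 to +0.35. A lagged analysis would thus carry a built-in sign opposite to the one that the pathway predicts.

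**The case against.** The strongest reply is that 2.2.1 is a therapeutic aim, worded like most of the other objectives, and that its closing phrase may only name the content of the group. Section 2.0 lists rising meaning and falling symptoms side by side with no link, and Table 1 gives the secondary variable simply as the level of depression and anxiety. No section states a mediation hypothesis. This stands. A reader might infer that the protocol poses a formal question about mechanism and then fails to answer it, and the documents do not support that reading. On the milder reading the phrase still credits one part of a package, so it still needs rewording.

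A reader might also infer that the planned tests say nothing about meaning. That goes too far. Section 9.2 gives Purpose in Life at baseline, Visit 4 and Visit 8 with both changes, so it would show whether mean meaning rose and roughly when. A flat mean would count against the phrase in the objective. Only the link within individuals is missing.

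Nor do the documents support a complaint that the study cannot tell which component to carry forward. Section 6.0 presents the combination as deliberate, and the uses named for future studies are the feasibility and attendance data (9.3.1, 9.3.2).

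Finally, 15 people are few for a correlation, and one would not separate meaning-making from ACT. Both points are right. They limit the optional analysis, but they do not affect the mismatch in wording or the role given to the Purpose in Life Test.

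**Conclusion.** The point holds as a mismatch between what 2.2.1 credits, what is delivered, and the role that 9.2 gives to the measure of meaning. With one cohort and no comparator, even the combined package cannot be shown to have caused a change, so the supportable statement is pre-post change among participants in the combined group.

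No sample-size or precision figure in the plan is shown wrong by this point. The impact is minor to moderate: the study is a pilot, the objective is secondary, and the correction lies in wording and classification. The correlation figures assume complete, independent pairs. They are a best case, because retention is itself an outcome (9.3.1) and participants share one group.

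**What to change.** 1. Reword 2.2.1, 5.1.2 and 9.2 to describe pre-post change in depression and anxiety among participants in the combined ACT and meaning-making group, without attributing it to meaning-making.
2. In Table 1 and 9.2, report the Purpose in Life Test separately as a measure of meaning (a process measure), not as an estimate of depression or anxiety. This leaves the CAS and Mini-MAC to carry the symptom objective. Section 6.2 describes neither as a depression scale, so the team should state which scores, including which Mini-MAC subscales, stand for depression.
3. Optionally, report the correlation across participants between baseline-to-post change in Purpose in Life and change in the CAS and Mini-MAC scores, with a 95% interval and the number of complete pairs. Label it descriptive. State that shared mood can produce it without any pathway, and that it does not separate meaning-making from ACT. Do not add a lagged analysis through the mid-point, for the reason in step 4 of the working.

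The cost is a text change and, if step 3 is taken, a few correlations on scores already scheduled at all three assessments. The downside is a more modest secondary claim and, for the optional part, a wide interval.
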